11.0 Data Quality Assurance

Computer logic and manual checks will be created to identify items such as inconsistent study dates. Any necessary corrections will be made to the eCRF.

12.0 Use of Information

Any research that may be done using optional pharmacogenetic exploratory research samples from this study will be experimental in nature and the results will not be suitable for clinical decision making or patient management. Hence, the subject will not be informed of individual results, should analyses be performed, nor will anyone not directly involved in this research. Correspondingly, researchers will have no access to subject identifiers. Individual results will not be reported to anyone not directly involved in this research other than for regulatory purposes. Aggregate data from optional pharmacogenetic exploratory research may be used in scientific publications or presented at medical conventions. Optional pharmacogenetic exploratory research information will be published or presented only in a way that does not identify any individual subject.

Appendix A. Responsibilities of the Clinical Investigator

Clinical research studies sponsored by AbbVie are subject to the Good Clinical Practices (GCP) and local regulations and guidelines governing the study at the site location. In signing the Investigator Agreement in Section 14.0 of this protocol, the investigator is agreeing to the following:

- 1. Conducting the study in accordance with the relevant, current protocol, making changes in a protocol only after notifying AbbVie, except when necessary to protect the safety, rights or welfare of subjects.
- 2. Personally conducting or supervising the described investigation(s).
- 3. Informing all subjects, or persons used as controls, that the drugs are being used for investigational purposes and complying with the requirements relating to informed consent and ethics committees (e.g., independent ethics committee [IEC] or institutional review board [IRB]) review and approval of the protocol and amendments.
- 4. Reporting adverse experiences that occur in the course of the investigation(s) to AbbVie and the site director.
- 5. Reading the information in the Investigator's Brochure/safety material provided, including the instructions for use and the potential risks and side effects of the investigational product(s).
- 6. Informing all associates, colleagues, and employees assisting in the conduct of the study about their obligations in meeting the above commitments.
- 7. Maintaining adequate and accurate records of the conduct of the study, making those records available for inspection by representatives of AbbVie and/or the appropriate regulatory agency, and retaining all study-related documents until notification from AbbVie.
- 8. Maintaining records demonstrating that an ethics committee reviewed and approved the initial clinical investigation and all amendments.

- 9. Reporting promptly, all changes in the research activity and all unanticipated problems involving risks to human subjects or others, to the appropriate individuals (e.g., coordinating investigator, institution director) and/or directly to the ethics committees and AbbVie.
- 10. Following the protocol and not make any changes in the research without ethics committee approval, except where necessary to eliminate apparent immediate hazards to human subjects.

ABT-493/ABT-530 M13-596 Protocol Amendment 2 EudraCT 2015-005616-14

Appendix C. Study Activities – Treatment Period

Activity	Screening	Day 1 ^a	Study Day 3	Wk 1	Optional Day 10 for Mgmt of Immuno- suppressive Meds	Wk 2	Wk 4	Wk 6	Wk 8	Wk 12 EOT or Premature D/C from Treatment	Unsched Visit for Mgmt of Immuno- suppressive Meds
Informed Consent ^c	×										
Medical History	X	×									
Physical Exam	×	×								X	
Vital Signs, Weight, Height	×	×	×	×	X	×	X	X	X	×	×
ECG	X										
Hematology/Chemistry/Urinalysis/Coagulation Panel	X	X	X	×	X	X	X	X	X	X	X
Pregnancy Test (serum [s] urine [u]) ^f	(s) X	(n) X					(n) X		(n) X	(n) X	
HBsAg, Anti-HCV Ab, Anti-HIV Ab	X										
Drug/Alcohol Screen	X										
Alpha fetoprotein	X										
Hemoglobin A1C ^g	X										
HCV Genotype and Subtype	X										
FibroTest and APRI or FibroScan or Liver Biopsy	X										
IL28B Sample ⁱ		X									
Optional Exploratory Pharmacogenetic Sample		X									
Total Insulin		×									

Activity	Screening	Day 1 ^a	Study Day 3	Wk 1	Optional Day 10 for Mgmt of Immuno- suppressive Meds	Wk 2	Wk 4	Wk 6	Wk 8	Wk 12 EOT or Premature D/C from Treatment	Unsched Visit for Mgmt of Immuno- suppressive Meds
Sample for cyclosporine, tacrolimus, everolimus, sirolimus therapeutic drug monitoring (Local Lab)	X	X	X	Х	X	X	X	×	X	X	×
Immunosuppressive Regimen Dose Modification Review		X	X	X	X	X	X	X	X	X	X
Immunosuppression Regimen Dosing Diary dispensation, review and collection	X (Dispense only)	X	X	X	X	X	X	X	X	X	X
Study Drug Dosing Card dispensation, review and collection		X (Dispense only)	X	X	X	X	X	X	X	X	
Concomitant Medication Assessment	X	X	X	X	X	X	X	X	X	X	X
Adverse Event Assessment	×	×	×	×	X	×	×	×	×	X	×
Patient Reported Outcomes Instruments (PROs) ^m		X								X	
Study Drugs Dispensed		X					X		X		
HCV RNA Samples	X	X	X	X	X	X	X	X	X	X	
Study Drug Accountability and Review of Study Drug Adherence			X				X		X	X	
HCV Resistance Sample		X	X	X	X	X	X	X	X	X	
Archive Plasma Sample	X	X	X	X	X	X	X	X	X	X	
Pharmacokinetic Samples DAA ^{c,p}		X _o	×	×	X	×	×°	×	×	X	

abbvie ABT-493/ABT-530 M13-596 Protocol Amendment 2 EudraCT 2015-005616-14

Wk = Week; EOT = End of treatment; D/C = Discontinuation

- All procedures to be performed prior to first dose, with the exception of the additional (optional) post-dose pharmacokinetic intensive samples (Section 5.3.2.1). a.
- Subjects who prematurely discontinue from the study during the Treatment Period should return to the site to complete the Premature D/C from Treatment Visit Procedures (preferably prior to the initiation of any other anti-HCV therapy)
- Subjects need to sign and date an IRB/IEC approved informed consent for the study (prior to performing any screening or study-specific procedures) and the optional pharmacogenetic and intensive pharmacokinetic sample(s), if applicable. ပ
- d. A complete medical history will be taken at Screening and will be updated at the Study Day 1 Visit.
- e. Height will be measured at the Screening Visit only.
- Pregnancy testing is not required for women not of childbearing potential as defined in Inclusion Criterion 2. Ŧ.
- g. For subjects with history of Diabetes Mellitus.
- For subjects who have not had a qualifying liver biopsy within the previous 6 months or a qualifying FibroScan within the previous 3 months. h.
- If the IL28 sample or the optional Pharmacogenetic sample are not collected at Study Day 1, they may be collected at any other visit during the study.
- Sample for cyclosporine, tacrolimus, everolimus, or sirolimus, blood concentrations at screening may take place as an unscheduled visit so the subjects screening day CNI/mTOR dose is not interrupted.
- and/or tacrolimus during the screening visit and subsequent visits as indicated. The diaries will be reviewed for completeness and accuracy between study visits and collected The Immunosuppression Regimen Dosing Diary will be provided to study subjects taking an immunosuppressive regimen containing cyclosporine, sirolimus, everolimus, by site staff after review. ¥
- See specific information regarding adverse event collection in Section 6.1.1.1.
- PROs should be administered before any study procedures and in the order listed as per Section 5.3.1.1. ï.
- Subjects should bring all study drug to every visit for the site to review adherence. However, the site will record the number of tablets returned only at the Study Drug Accountability Visits at Weeks 4, 8 and 12 or Premature D/C. n.
- For subjects participating in Optional Intensive PK sampling, intensive PK samples will be drawn on Day 1 at 2, 4 and 6 hours post-dose and on Week 4 at 0 (immediately prior to dose), 2, and 4 hours post the dose administered during the visit. Subjects not participating in intensive PK will not have a sample drawn at Day 1. o.
- p. Detail regarding timing of samples is provided in Section 5.3.2.1.

Appendix D. Study Activities – Post-Treatment (PT) Period

Activity	PT Day 3	PT Wk	PT Wk	PT Wk	PT Wk	PT Wk	PT Wk 24 or PT D/C ^a	Unsched Visit for Mgmt of Immunosuppressive Meds
Vital Signs and Weight	X	X	X	X	X	X	×	X
Hematology/Chemistry/Urinalysis/Coagulation Panel	×	X	X	X			×	X
Pregnancy Test (urine) ^b				(n) X			(n) X	
PRO Instruments ^c						X	X	
Concomitant Medication Assessment	X	X	X	X^{q}	X^{q}	X^{q}	X^{q}	X^{d}
Adverse Event Assessment ^{e,f}	X	X	$X_{\rm e}$	X	X	X	X	X
HCV RNA Samples			X	X	X	X	×	
HCV Resistance Sample			X	X	X	X	X	
Cyclosporine, tacrolimus, everolimus, sirolimus therapeutic drug monitoring (Local Lab)	X	X	X	X				X
Immunosuppression Regimen Dosing Diary dispensation, review and collection [§]	X	X	X	X				X
Archive Plasma Sample	X	X	X	X	X	X	X	

Wk = Week; PT D/C = Post-Treatment Discontinuation

Subjects who prematurely discontinue from the Post-Treatment Period should return to the site to complete the PT D/C Visit procedures. ä.

Urine pregnancy testing is not required in the PT Period for women that are not of childbearing potential.

PROs should be administered before any study procedures and in the order listed as per Section 5.3.1.1.

d. Only medications taken for SAEs and for treatment of HCV will be collected after 30 days post-dosing.

- EudraCT 2015-005616-14
- Nonserious AEs and all SAEs will be collected until 30 days post dosing.
- Only SAEs will be collected after the 30 days post dosing (see Section 6.1.4). ų.
- and/or tacrolimus during the screening visit and subsequent visits as indicated. The diaries will be reviewed for completeness and accuracy between study visits and collected The Immunosuppression Regimen Dosing Diary will be provided to study subjects taking an immunosuppressive regimen containing cyclosporine, sirolimus, everolimus, by site staff after review. à

Day 1 of the Post-Treatment Period will be defined as the day after the last dose of study drug. Note:

abbvie ABT-493/ABT-530

M13-596 Protocol Amendment 2 EudraCT 2015-005616-14

Appendix E. **Protocol Amendment: List of Changes**

The summary of changes is listed in Section 1.1.

Specific Protocol Changes:

Section 3.0 Introduction Subsection DDI STUDIES WITH CYCLOSPORINE AND TACROLIMUS Fifth paragraph, bullet previously read:

The dose of cyclosporine with ABT-493/ABT-530 (300/120 mg QD) should not exceed 100 mg once daily

Has been changed to read:

The dose of cyclosporine with ABT-493/ABT-530 (300/120 mg QD) should not exceed 100 mg once daily for entry into the study. If the cyclosporine maintenance dose needs to be increased to a total daily dose greater than 100 mg during the Treatment Period, discussion with the Therapeutic Area Medical Director should occur. Dosages of cyclosporine > 400 mg are not allowed during the Treatment Period.

Section 5.1.2 Treatment Period Second paragraph, first sentence previously read:

Subject immunosuppression dosing regimen diaries will be maintained throughout the trial, for all subjects taking cyclosporine, sirolimus, everolimus, and/or tacrolimus during both the Treatment and Post-Treatment periods.

Has been changed to read:

Subject immunosuppression dosing regimen diaries will be maintained throughout the trial, for all subjects taking cyclosporine, sirolimus, everolimus, and/or tacrolimus during the Screening, Treatment and Post-Treatment periods.

abbvie ABT-493/ABT-530

M13-596 Protocol Amendment 2 EudraCT 2015-005616-14

Section 5.2.1 Inclusion Criteria Criterion 3, last sentence previously read:

Females of non-childbearing potential (either postmenopausal or permanently surgically sterile as defined above) at Screening do not require pregnancy testing.

Has been changed to read:

Females of non-childbearing potential (either postmenopausal or permanently surgically sterile as defined in Section 5.2.4) at Screening do not require pregnancy testing.

Section 5.2.2 Exclusion Criteria **Criterion 7 previously read:**

Any cause of liver disease other than chronic HCV infection including but not limited to the following:

Has been changed to read:

Any cause of liver disease post transplantation other than chronic HCV infection including but not limited to the following:

Section 5.2.2 Exclusion Criteria Criterion 9, second bullet previously read:

Albumin < 3.5 mg/dL

Has been changed to read:

Albumin < 3.5 g/dL

Section 5.2.3.2 Management of Immunosuppressant Agent Dosing Third paragraph, bullet previously read:

3.0 Introduction

This statistical analysis plan (SAP) describes the statistical analyses to be completed by the AbbVie Statistics and Statistical Programming Departments, or designee, for Study M13-596. Study M13-596 examines the safety and efficacy of 12 weeks of treatment with the ABT-493/ABT-530 combination regimen in adults with HCV GT1 – 6 infection who are DAA-naïve and post primary orthotopic liver transplant or renal transplant.

This SAP (Version 1.0) provides details to further elaborate the statistical methods outlined in Clinical Study Protocol M13-596 Amendment 1 dated 26 May 2016 and describes analysis conventions to guide the statistical programming. Analyses will be performed using SAS[®] Version 9.3 (SAS Institute, Inc., Cary, NC) or later under the UNIX operating system.

4.0 Study Objectives, Design and Procedures

4.1 Objectives

The primary objectives of this study are to compare the 12-week sustained virologic response, SVR_{12} (HCV RNA < LLOQ 12 weeks following therapy) of 12 weeks of treatment with the ABT-493/ABT-530 combination regimen in adults with HCV GT1 – 6 infection and post primary orthotopic liver transplant or renal transplant to a pre-defined threshold, based on the historical SVR_{12} rates for the current standard of care regimens (sofosbuvir/ledipasvir plus ribavirin or sofosbuvir plus daclatasvir plus RBV) and to assess the safety of treatment with the ABT-493/ABT-530 combination regimen for 12 weeks in adults with HCV GT1 – 6 infection and post primary orthotopic liver transplant or renal transplant.

The secondary objectives are to assess the percentage of subjects with on-treatment virologic failure, and the percentage of subjects with post-treatment relapse.

The pharmacokinetics and the emergence and persistence of viral variants for this treatment regimen also will be assessed.

4.2 Design Diagram

This is a Phase 3, single arm, open-label, multicenter study evaluating the safety and efficacy of ABT-493/ABT-530 for 12 weeks, in GT1 – 6 HCV-infected non-cirrhotic (F0-F3) subjects who have received a primary orthotopic liver or renal transplant who are either HCV treatment-naïve or prior treatment-experienced with IFN or pegIFN with or without RBV or sofosbuvir with RBV with or without pegIFN (except GT3-infected subjects who must be treatment-naïve).

This study consists of a Treatment Period and a Post-Treatment (PT) Period.

The study is designed to enroll approximately 90 subjects to meet scientific and regulatory objectives without enrolling an undue number of subjects in alignment with scientific and ethical considerations.

Figure 1. Study Schematic

4.3 Sample Size

It is planned to enroll approximately 90 subjects with a minimum of 15 post-renal transplant subjects and a maximum of approximately 50 subjects with HCV genotype 1 infection in this study. The primary efficacy endpoint of SVR₁₂ will be assessed for the ITT population. For the primary efficacy endpoint of SVR₁₂, with a sample size of 90 subjects and assuming that 96% of the subjects will achieve SVR₁₂, this study has

greater than 90% power to show non-inferiority to the historical SVR_{12} rate of 94% (based on the lower bound of a normal approximation of a single binomial proportion confidence interval being above a threshold of 86%) using a one-sample test for superiority using EAST 6.3.

The 86% threshold was established by applying an 8% non-inferiority margin to the historical SVR₁₂ rate of 94%

No adjustment for dropouts is applicable because subjects who do not have data at Post-Treatment Week 12 (after imputing) are counted as failures for SVR_{12} .

4.3.1 Justification of Non-Inferiority Margin for SVR₁₂

The 8% non-inferiority margin is based on the paucity of data in non-GT1 liver transplant recipients and renal transplant recipients regardless of genotype and the potential benefit of a RBV-free regimen.

- Most data published on the post-transplant population to date, including the studies that were used to establish the historical control rate for this study, are in GT1 subjects who have received a liver transplant.
- The current standard-of-care regimens used for historical comparison all include RBV. Given the ABT-493/ABT-530 regimen is RBV-sparing, a slightly wider non-inferiority margin compared to the margin used in other AbbVie Phase 3 studies with ABT-494/ABT-530 was considered, as a small decrement in efficacy may be outweighed by an improvement in safety offered with the avoidance of RBV in a patient population more susceptible to RBV related toxicity.

4.4 Primary Analyses

The primary analysis will occur after all subjects have completed the PT Week 12 Visit or prematurely discontinued the study. For the primary analysis, data will be locked after performing data cleaning. Results from the primary analysis (e.g., SVR₁₂ data) will be described in the primary clinical study report (CSR) that is planned to be included as part of submissions to regulatory agencies to support possible labeling changes.

The final analysis will be conducted when all subjects enrolled in the study have completed the 24 week post-treatment visit or prematurely discontinued from the study. Data after the primary analysis will be added to a new version of the database which will be cleaned and locked at the end of the study and included in the final CSR.

5.0 Analysis Populations

5.1 Definition for Analysis Populations

5.1.1 Intention-to-Treat (ITT) Population

All enrolled subjects who receive at least one dose of study drug will be included in the ITT population. Efficacy analyses will be performed on the ITT population.

5.1.2 Modified Intention-to-Treat (mITT) Populations

Sensitivity analyses of SVR₁₂ as described in Section 10.5, when applicable, will be performed on the ITT population modified to exclude subjects not of an eligible genotype (e.g., subjects of multiple/mixed genotypes or treatment-experienced subjects who were determined to be GT3 according to LiPA, Sanger or phylogenetic analyses as described in Section 10.8 under HCV Genotype/Subtype) (mITT-GT), and on the mITT-GT population further modified to exclude subjects who did not achieve SVR₁₂ for reasons other than virologic failure (mITT-GT-VF).

5.1.3 Safety Population

All subjects who receive at least one dose of study drug will be included in the safety population. Safety and demographic analyses will be performed on the safety population.

5.2 Variables Used for Stratification of Randomization

This study is not randomized. Eligible subjects will be enrolled into a single arm.

conventions
conventions

6.1 Definition of Baseline and End of Treatment Assessment

6.1.1 Baseline

The baseline value refers to the last non-missing measurement collected before the first dose of study drug is received. The protocol specifies that all Day 1 assessments (other than optional intensive PK samples) are to be performed prior to administering the first dose of study drug. Therefore, all Day 1 assessments for which time is not collected will be assumed to be pre-dose and the baseline value will be the last non-missing measurement collected on or before the first day of study drug administration.

All Day 1 assessments with time available must be before the time of first dose to be considered baseline and the last non-missing measurement collected before the date and time of the first dose of study drug will be considered the baseline value. If multiple measurements that are prior to dosing are recorded on the same date and with the same time or if time is not available, then the average of these measurements will be considered the baseline value. The same baseline value will be used for analyses of the Treatment and Post-Treatment Periods.

Safety assessments that are related to a serious adverse event that occurred on the first dose day are excluded when applying this algorithm.

6.1.2 Study Days

Study days are calculated for each time point relative to the first dose of study drug. Study days are negative values when the time point of interest is prior to the first study drug dose day. Study days are positive values when the time point of interest is after the first study drug dose day. There is no Study Day 0. Study Day 1 is the day of the first dose of study drug.

Study Drug End Days (Days Relative to the Last Dose of Study Drug)

Study drug end days are calculated for each time point relative to the last dose of study drug. The last day of study drug dosing is defined as Study Drug End Day 0. Days before it have negative study drug end days and days after it have positive study drug end days.

Final Treatment Value

The final treatment value is defined as the last non-missing measurement collected after Study Day 1 and on or before Study Drug End Day 2.

Final Post-Treatment Value

The final post-treatment value for each subject is the last non-missing measurement collected after Study Drug End Day 2 and on or before Study Drug End Day 999.

6.2 Definition of Analysis Windows

For efficacy analyses of HCV RNA and resistance, the time windows specified in Table 1 and Table 2 describe how efficacy data are assigned to protocol-specified time points during the Treatment and PT Periods, respectively. All time points and corresponding time windows are defined based on the date/time of blood sample collection.

For laboratory data vital signs and PRO measurements, the time windows specified in Table 1 and Table 3 describes how data are assigned to protocol specified time points.

If more than one assessment is included in a time window, the assessment closest (except in analyses of SVR) to the nominal time will be used. If there are two observations equally distant to the nominal time, the latest one will be used in analyses. For analyses of SVR (e.g., SVR₁₂), the last value in the window will be used.

If multiple measurements are made on the same day for a safety laboratory parameter or a vital sign parameter, the average of the values will be used to calculate descriptive statistics and in analyses of the mean change from baseline. For summaries of shifts from baseline and potentially clinically significant values, multiple values on the same day will not be averaged; all values will be considered for these analyses.

Scheduled Visit	Nominal Day (Study Day)	Time Window (Study Day Range)	
Day 1/Baseline ^a	1	$\leq 1^a$	
Day 3	3	2 to 5	
Week 1	7	6 to 8	
Day 10	10	9 to 12	
Week 2	14	13 to 21	
Week 4	28	22 to 42	
Week 6	42	43 to 49	
Week 8	56	50 to 70	
Week 12	84	71 to 98	
Final Treatment Visit ^b	2 to \leq 2 days after	2 to \leq 2 days after last dose of study drug	

Table 1.Analysis Time Windows for HCV RNA, Resistance Endpoints,
Laboratory, Vital Sign Measurements and PRO Instruments
(Treatment Period)

a. Day of first dose of study drug.

b. The last value within the window will be used to define the Final Treatment Visit value. The upper bound of this Final window is Study Drug End Day ≤ 2 .

Note: Data must also have Study Drug End Day ≤ 2 for all windows. The result closest to the scheduled time point will be used. PRO instruments are collected at Day 1 and End of Treatment Visit (Week 12) only.

Table 2.Analysis Time Windows for HCV RNA and Resistance Endpoints
(Post-Treatment Period)

Scheduled Visit ^a	Nominal Day (Study Drug End Day)	Time Window (Study Drug End Day Range)
Post-Treatment Week 2	14	3 to 21
Post-Treatment Week 4	28	22 to 42
Post-Treatment Week 8	56	43 to 70
Post-Treatment Week 12	84	71 to 126
Post-Treatment Week 24	168	127 to 999
SVR ₄ ^b	28	3 to 56
SVR ₁₂ ^b	84	57 to 126
SVR ₂₄ ^b	168	127 to 210

a. Post-Treatment Visits are applicable for subjects who received at least one dose of study drug.

b. For SVR windows, the last value in the window will be used.

Note: The result closest to the scheduled time point will be used, except for SVR₄, SVR₁₂, and SVR₂₄. Data must also have Study Drug End Day > 2 for all windows. Study Drug End Day 0 is defined as the day of the last dose of study drug.

Table 3.Laboratory Data, Vital Sign and PRO Instruments Visit Windows
(Post-Treatment Period)

	Nominal Day	Time Window (Study Drug End Days Range)
Scheduled Time	(Study Drug End Day)	Vital Sign
Post-Treatment Day 3	3	3 to 5
Post-Treatment Week 1	7	6 to 10
Post-Treatment Week 2	14	11 to 21
Post-Treatment Week 4	28	22 to 42
Post-Treatment Week 8	56	43 to 70
Post-Treatment Week 12	84	71 to 126
Post-Treatment Week 24	168	127 to 999
Final Post-Treatment Visit ^a	> 2 days aft	er last dose of study drug

a. The last value within the Post-Treatment Period window will be used to define the final post-treatment value. The lower bound of this Final window is Study Drug End Day 3.

Note: The result closest to the scheduled time point will be used. Data must also have Study Drug End Day > 2. Vital signs are collected at every PT visit; hematology, chemistry, urinalysis, and coagulation panels are collected at every PT visit except PTW8 and PTW12. PRO instruments are collected at PTW12 and PTW24 (or PTDC) only.

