10.0 Efficacy Analysis

10.1 General Considerations

General Considerations

All efficacy analyses will be performed on the ITT population, unless otherwise specified.

Missing data will be imputed as described in Section 6.3 for analyses of the HCV RNA endpoints of SVR.

Plasma HCV RNA levels will be determined for each sample collected by the central laboratory using the Roche COBAS[®] AmpliPrep/COBAS[®] TaqMan[®] HCV Quantitative Test, v2.0. The lower limit of detection (LLOD) and lower limit of quantification (LLOQ) for this assay (regardless of genotype) are both 15 IU/mL.

HCV RNA results that are detectable but not quantifiable are reported as "< 15 IU/ML HCV RNA DETECTED" and those that are undetectable are reported as "HCV RNA NOT DETECTED" in the database.

The notation "HCV RNA < LLOQ" is used to represent all HCV RNA values < 15 IU/mL, including values reported as "HCV RNA NOT DETECTED" or "< 15 IU/ML HCV RNA DETECTED." HCV RNA ≥ LLOQ are all quantifiable values of 15 IU/mL or greater.

Definitions for Efficacy Endpoints

A confirmed quantifiable value during treatment is defined as any two consecutive HCV RNA measurements \geq LLOQ (or 100 IU/mL for **Breakthrough**), either both during treatment or at the final treatment measurement and the next consecutive post-treatment measurement. A confirmed quantifiable post-treatment value is defined as any two consecutive post-treatment HCV RNA measurements \geq LLOQ.

Breakthrough = confirmed HCV RNA \geq 100 IU/mL after HCV RNA < LLOQ during the Treatment Period; or confirmed increase from nadir in HCV RNA (two consecutive

HCV RNA measurements > 1 \log_{10} IU/mL above nadir) at any time point during the Treatment Period. A single breakthrough value (≥ 100 IU/mL or > 1 \log_{10} above nadir) followed by lost to follow-up also will be considered a breakthrough (i.e., will not require confirmation).

EOT failure = HCV RNA \geq LLOQ at end of treatment with at least 6 weeks of treatment, where the HCV RNA value must be collected on or after Study Drug Day 36 and study drug duration \geq 36 days.

On-treatment virologic failure = Breakthrough or **EOT failure**.

 $SVR_4 = HCV RNA < LLOQ$ in the SVR_4 window (4 weeks after the last actual dose of study drug) without any confirmed quantifiable ($\geq LLOQ$) post-treatment value before or during that SVR window.

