10.7 Additional Efficacy Analyses

The following additional efficacy endpoints will be summarized:

- The percentage of subjects with HCV RNA < LLOQ at each post-baseline visit in the Treatment Period (using data as observed);
- The percentage of DAA-naïve subjects with on-treatment virologic failure;
- The percentage of DAA-naïve subjects with post-treatment relapse;
- The percentage of subjects with SVR₄;
- The percentage of subjects with SVR₂₄;

- The percentage of subjects who relapsed after achieving SVR₁₂ (**Relapse₂₄**);
- The percentage of subjects with virologic failure through Post-Treatment Week 12 (i.e., the SVR₁₂ non-responders due to on-treatment virologic failure or Relapse₁₂)

In the above analyses for SVR, virologic failure, and relapse, the percentage of subjects with a two-sided 95% Wilson score interval will be summarized. Imputations for missing data will be performed as described in Section 6.3 for analysis of SVR, where a missing response will be imputed as a failure after performing the described imputation. All other endpoints will be presented using data as observed.

A summary of the subjects who completed treatment and relapsed (defined as **Relapse_{overall}**) will be prepared displaying the number of subjects relapsing overall and by SVR visit window (within the SVR₄, SVR₁₂, SVR₂₄ windows or after SVR₂₄ window), including the subject number and the SVR visit window corresponding to the first occurrence of relapse. A similar listing will be prepared for subjects who prematurely discontinued treatment and relapsed after having HCV RNA < LLOQ at their Final Treatment Visit.

The number and percentage of subjects who do not achieve SVR_{12} will be summarized by reason for non-response (as defined in Section 10.1). A listing of subject numbers and reason for non-response will be prepared. A similar summary and listing will be prepared for subjects who do not achieve SVR_{24} .

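### SAP Table 1 leaves Week 6's nominal Day 42 outside the Week 6 window, so Week 6 samples taken by Day 42 count as Week 4 in by-visit summaries

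*SAP*

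**What the plan says.** Three consecutive rows of SAP Section 6.2, Table 1, matter here. Each gives the visit, its nominal Study Day and its window:

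- "Week 4 28 22 to 42"
- "Week 6 42 43 to 49"
- "Week 8 56 50 to 70"

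The same section says how a result reaches a row: "All time points and corresponding time windows are defined based on the date/time of blood sample collection". The visit label on the case report form therefore plays no part. Where a window holds several results, one is chosen: "If more than one assessment is included in a time window, the assessment closest (except in analyses of SVR) to the nominal time" is the one used, and ties go to the later result.

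The protocol makes Week 6 a scheduled visit, and its Appendix C collects HCV RNA, laboratory tests and vital signs there. SAP Section 10.7 then reports "The percentage of subjects with HCV RNA < LLOQ at each post-baseline visit in the Treatment Period (using data as observed"). SAP Sections 11.3.2 and 11.4.2 report mean change from baseline at each post-baseline visit for laboratory values and vital signs. Neither document makes an exception for Week 6.

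**The concern.** A visit window should contain the day on which the plan says the visit is due. Week 6 is due on Day 42, but its window opens on Day 43, so a subject seen exactly on the nominal day is not counted at Week 6. Nor is one seen a few days early.

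At stake is the content of two rows in each by-visit table. The Week 6 row would hold only samples taken after the nominal day, from a reduced number of subjects. The Week 4 row could include some values taken about two weeks late. There is also a traceability problem. Literal programming yields a thinned Week 6 row, while a programmer who corrects the windows without saying so produces outputs that depart from the signed plan.

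**Working it through.** **Inputs.** Nominal days and windows come from SAP Tables 1 to 3. Study-day numbering comes from SAP Section 6.1.2 (first dose is Day 1, no Day 0). The selection rule comes from SAP Section 6.2.

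**Step 1: does each window contain its own nominal day?** Leaving aside the baseline and final-visit rows, Tables 1, 2 and 3 have 8 + 8 + 7 = 23 numeric rows. In 22 of them the nominal day lies inside the window. The exception is Week 6 in Table 1, where 42 < 43.

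**Step 2: what rule built Table 1?** Take each upper limit as the midpoint of adjacent nominal days, rounded down.

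| Adjacent visits | Midpoint | Upper limit in Table 1 |
|---|---|---|
| Day 3 / Week 1 | (3 + 7)/2 = 5 | 5 |
| Week 1 / Day 10 | (7 + 10)/2 = 8.5, so 8 | 8 |
| Day 10 / Week 2 | (10 + 14)/2 = 12 | 12 |
| Week 2 / Week 4 | (14 + 28)/2 = 21 | 21 |
| Week 4 / Week 6 | (28 + 42)/2 = 35 | **42** |
| Week 6 / Week 8 | (42 + 56)/2 = 49 | 49 |
| Week 8 / Week 12 | (56 + 84)/2 = 70 | 70 |

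Six of the seven limits are reproduced. The seventh, Day 42, is the midpoint of Weeks 4 and 8: (28 + 56)/2 = 42. That is the limit one would set if there were no Week 6 visit. The post-treatment windows in Table 2, which have no Week 6, do run 22–42 for Week 4 and 43–70 for Week 8. The likely explanation, which is an inference, is that Week 6 was added by splitting 43–70 at Day 49 while the Week 4 limit was left alone.

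**Step 3: apply the SAP's selection rule to example subjects.**

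| Sample days around Weeks 4 to 8 | As written | With Week 4 = 22–35, Week 6 = 36–49 |
|---|---|---|
| 28, 42, 56 | Week 4 = Day 28; Week 6 empty; Day 42 unused | Week 4 = Day 28; Week 6 = Day 42 |
| 42, 56 (Week 4 missed) | Week 4 = Day 42; Week 6 empty | Week 4 empty; Week 6 = Day 42 |
| 28, 39, 56 | Week 4 = Day 28; Week 6 empty; Day 39 unused | Week 4 = Day 28; Week 6 = Day 39 |
| 28, 43, 56 | Week 4 = Day 28; Week 6 = Day 43 | Same |
| 28, 45, 56 | Week 4 = Day 28; Week 6 = Day 45 | Same |

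**Step 4: how many samples might move?** The documents give no visit tolerance and no spread of visit days, so this step is illustrative. Assume visit days are normal with mean μ and standard deviation SD. Then P(day ≤ 42) = Φ((42.5 − μ)/SD).

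| SD (days) | μ = 42 (the SAP's nominal day) | μ = 43 (six calendar weeks after Day 1) |
|---|---|---|
| 1.5 | Φ(0.333) = 0.631 | Φ(−0.333) = 0.369 |
| 2 | Φ(0.25) = 0.599 | Φ(−0.25) = 0.401 |
| 3 | Φ(0.167) = 0.566 | Φ(−0.167) = 0.434 |

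If all 90 planned subjects attended Week 6, the extremes would be 0.369 × 90 ≈ 33 and 0.631 × 90 ≈ 57 subjects. These are not bounds. With SD 1 the same formula gives Φ(−0.5) = 0.309 and Φ(0.5) = 0.691, both outside that range.

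**The case against.** The strongest reply is about scheduling. There is no Day 0, so a visit exactly six calendar weeks after first dose falls on Study Day 43, inside the window. Sites that book the same weekday as Day 1 would keep most Week 6 samples in the right row. This stands and limits the size of the effect. It does not remove the contradiction, because the SAP's own nominal day is 42 and any visit before Day 43 is still misassigned.

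A reader might also infer more than the documents support:

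- **That the data are lost altogether, or that the main endpoints are affected.** SVR12 uses the post-treatment windows in Table 2. Breakthrough is judged on consecutive measurements at any time on treatment, end-of-treatment failure on the end-of-treatment value, and relapse on post-treatment values. Maximum toxicity grade, the hepatic criteria and potentially clinically significant vital signs draw on on-treatment values regardless of visit row.
- **That resistance results are affected, because the title of Table 1 names them.** SAP Section 10.8 uses baseline, the sample closest after failure or discontinuation, and 24 weeks post-treatment. It specifies no Week 6 resistance summary.
- **That SAP Section 10.1 contradicts Table 1.** Its end-of-treatment failure definition reads "with at least 6 weeks of treatment, where the HCV RNA value must be collected on or after Study Drug Day 36". That is a minimum-duration condition, not a visit window, and both rules can apply to one sample. Day 36 fits the proposed window but is not a second inconsistency.
- **That Week 4 viral response is inflated.** This needs a missing Week 4 sample together with a Week 6 sample taken by Day 42. No missed-visit rate is given, so it is possible but not established.

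**Conclusion.** The point holds as an internal contradiction in SAP Table 1, and that part needs no assumption: the Week 6 window excludes the Week 6 nominal day. Its reach is limited to descriptive by-visit outputs, namely the percentage with HCV RNA below LLOQ at each on-treatment visit (SAP Section 10.7) and mean changes in laboratory values and vital signs (SAP Sections 11.3.2 and 11.4.2). No success criterion rests on these.

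The number of subjects affected cannot be derived from the documents. The 37–43% and 57–63% figures rest on assumed normal visit days, SD 1.5 to 3, centred on Day 43 and Day 42 respectively. They show that the loss from the Week 6 row could be substantial, and that it depends on how sites book visits. The correction is worth making, at modest priority.

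**What to change.** In SAP Section 6.2, Table 1, change the Week 4 window to Days 22–35 and the Week 6 window to Days 36–49. Leave Week 8 at Days 50–70. This puts Day 42 inside its own window and restores the midpoint rule that every other boundary in the table follows.

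Make the change in a dated SAP revision before the database lock for the primary analysis, so that the programmed windows and the written plan agree. The cost is two table cells and the matching programming specification. Data collection, the visit schedule and the protocol do not change.
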